4.2.4 Immunological data

The rules for handling BLQ or ALQ measurements for all immunological data will be as described in [Section 4.2.2](#).

Descriptive statistics will be calculated if at most 33% of the individual data points at a time point are missing or are either not quantifiable (<LLOQ) or ALQ as described in [Section 4.2.2](#).

4.2.5 UCB7665 concentration data

Measurements that are BLQ will be imputed with half of the LLOQ for the purpose of calculating the geoMean and its 95% CI, the geoCV, the arithmetic mean, and SD for summaries and figures. If any summary value (geoMean, arithmetic mean, lower CI level or minimum) is lower than LLOQ, then 'BLQ' will be displayed.

For the individual figures, any concentrations that are BLQ will be regarded as missing, with the exception of predose measurements BLQ on Day 1, which will be imputed with zero for linear scale plots.

Additional rules for PK data summaries are provided in [Section 9.1](#).

4.2.6 Electrocardiogram data

For the ECG data, all calculations of changes from Baseline and descriptive statistics will be based on the mean of the triplicate assessments at each time point. In the event that there are not 3 available measurements at a given time point, the mean will be calculated based on the number of measurements for which data is provided.

4.2.7 Dates and times

Partial dates may be imputed for the following reasons:

- Classification of Adverse events (AEs) as treatment-emergent
- Classification of medications as prior or concomitant

The following rules will be applied for partial start dates/times:

- If only start month and year are specified and not the same as month and year of first dosing then use the 1st of the month, or the date of screening if this is later (if the latter imputation results in an end date that is earlier than the start date, then use the 1st of the month). If time is missing this will be imputed as 00:00 h;
- If only the month and year are specified and the month and year of first dosing is the same as the month and year of the start date, then use the date of first dosing. If this results in an imputed start date that is after the specified end date, then use the 1st of the start month, or the date of screening if this is later (if the latter imputation results in an end date that is earlier than the start date, then use the 1st of the month). If the imputed date is the date of first dosing then time will be imputed as the start time of the infusion (ie, event will be regarded as treatment-emergent);
- If only the year is specified, and the year of dosing is not the same as the year of the start date then use January 01 of the year of the start date. If time is missing this will be imputed as 00:00 h;
- If only the year is specified, and the year of dosing is the same as the year of the start date, then use the date of first dosing. If this results in an imputed start date that is after the specified end date, then use January 01 of the year of the start date, or the date of screening if this is later (if the latter imputation results in an end date that is earlier than the start date, then use January 01). If the imputed date is the date of first dosing then time will be imputed as the start time of the infusion (ie, event will be regarded as treatment-emergent);

- If the start date is completely unknown, then use the date of first dosing. If this results in an imputed start date that is after the specified end date, then use January 01 of the year of the end date, or the date of screening if this is later (if the latter imputation results in an end date that is earlier than the start date, then use January 01). If the imputed date is the date of first dosing then time will be imputed as the start time of the infusion (ie, event will be regarded as treatment-emergent).

Start and end time is not recorded for concomitant medications, thus no imputations for missing times will be performed. Any medication with a start date on the first dosing date, will be assumed to be concomitant.

The following rules will be applied for partial stop dates:

- If only the month and year are specified, then use the last day of the month;
- If only the year is specified, then use December 31 of the known year;
- If the stop date is completely unknown, do not impute the stop date

Missing or partially missing date and/or times will be imputed as described in [Table 4-1](#) for the calculation of duration of each AE. Adverse event duration is computed in and reported in day and time format: xx d hh:mm.

Table 4-1: Calculation rules for duration of AEs

Data availability	Onset date/time	Outcome date/time	Calculation rules
Complete data	D1/T1	D2/T2	Duration = [(D2 - D1)*24 + (T2 - T1)]/24 d
End time missing	D1/T1	D2/--	End time is substituted by time 23:59h (=23.98 in decimal format) Duration = <[(D2 - D1)*24 + (23.98 - T1)]/24 d
Start time missing	D1/--	D2/T2	Onset time is substituted by time 00:00h.
Start and end time missing	D1/--	D2/--	Duration = <D2 - D1 + 1
Start day and time missing	--	D2/T2	Duration = <[(D2 - D0)*24 + (T2 - T0)]/24 d For a subject in the SS, D0 and T0 are the date and time of first administration of UCB7665 and for screen failures, D0 is the date of the screening visit and T0 = 00:00h

Table 4–1: Calculation rules for duration of AEs

Data availability	Onset date/time	Outcome date/time	Calculation rules
End day and time missing	D1/T1	--/--	
For ongoing AE: Duration = >Discharge day – D1 d OR
 
For resolved AE: Duration = <Discharge day – D1 d OR
 
Where discharge refers to the date of the end of study visit for completed subjects or the date of discontinuation for subjects that were withdrawn.
 
For any AEs with known start date/time after the date of discontinuation, the date of last contact will be used as the discharge day.

Start and end date missing	--/--	--/--	
For ongoing AE: Duration = >Discharge day – D0 d OR
 
For resolved AE: Duration = <Discharge day – D0 d OR
 
For a subject in the SS, D0 and T0 are the date and time of first administration of UCB7665 and for screen failures, D0 is the date of the screening visit and T0 = 00:00h.
 
Discharge refers to the date of the end of study visit or the date of discontinuation for subjects that were withdrawn.
 
For any AEs with known start date/time after the date of discontinuation, the date of last contact will be used as the discharge day.

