6.2 Other Baseline characteristics

MG medication (medication where indication is MG), MGFA disease class and thymectomy (yes/no) at baseline will be listed and summarized by treatment group for the RS.

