6.4.3 Concomitant medication definition

Concomitant medications will include any medication that has been taken at least once (after the first administration of IMP) during the Dosing Periods and/or the Observation Period.

Any medication that started prior to the first administration of IMP and continued after dosing will be classified as prior and concomitant. Any medication that started after the first administration of IMP in Dosing Period 1 will be classified as concomitant only.

Any medications with missing dates and/or times will be handled as described in [Section 4.2.7](#) in order to classify them as prior or concomitant.

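### Date imputation built for adverse events moves ongoing background medication with an unknown start out of the prior-and-concomitant table

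*SAP*

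**What the plan says.** SAP 4.2.7 gives two purposes for imputing partial dates: deciding whether an adverse event is treatment-emergent, and "Classification of medications as prior or concomitant". One list of start-date rules serves both. Three of them return the date of first dosing:

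- Wholly unknown start: "If the start date is completely unknown, then use the date of first dosing".
- Year only, in the dosing year: if "the year of dosing is the same as the year of the start date, then use the date of first dosing".
- Month and year only, in the dosing month: the same substitution is made.

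The one exception is a recorded end date that falls before the imputed start; an earlier date is then used. The section adds that medication times are not collected, and then: "Any medication with a start date on the first dosing date, will be assumed to be concomitant".

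SAP 6.4.2 defines prior medication as starting before the first administration of study drug. SAP 6.4.3 puts a drug in the prior-and-concomitant category when it started before that point and continued after it. A drug started after that point "will be classified as concomitant only". For missing dates 6.4.3 points back to 4.2.7, with no override. SAP 6.4 tabulates past, prior-and-concomitant and concomitant medication separately, by treatment group, on the Randomized Set.

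SAP 6.2 separately summarizes "MG medication (medication where indication is MG), MGFA disease class and thymectomy (yes/no) at baseline". It does not say how use at baseline is established when a start date is missing.

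**The concern.** Dating an unknown adverse event to the first dose is cautious, because it counts the event against treatment. The rule is written in those terms: its closing remark is that the event is then regarded as treatment-emergent, which has no meaning for a drug.

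For chronic therapy the same step discards information the trial holds. The protocol collects prior and concomitant medication at Visit 1 (8.1.1) and again predose at Visit 2 (8.2.1). Exclusion criterion 28 requires stable regimens of the drugs in Table 7.1. A long-standing immunosuppressant or cholinesterase inhibitor whose start the subject cannot recall is thus documented as in use before dosing, yet the derived date says it began at the first infusion.

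At stake is the description of background MG therapy by arm. With about 42 subjects, readers will look at that table when judging whether the arms were comparable.

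**Working it through.** There is no figure in the plan to reproduce; the point is how a stated rule classifies a record. The 4.2.7 rules and the 6.4 definitions were coded and run on test records. The dates are illustrative assumptions: Screening 1 March 2018, first infusion 20 March 2018.

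**Rules applied**

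1. Impute the start by 4.2.7, including the exception for an end date before the imputed start.
2. Prior if the imputed start is before 20 March 2018. A start on that day is not prior (6.4.2 and the same-day sentence in 4.2.7).
3. Concomitant if ongoing, or ended on or after 20 March 2018.
4. Prior but not concomitant is past.

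| Record | Imputed start | Class |
|---|---|---|
| Unknown start, ongoing | 20 Mar 2018 | concomitant, not prior |
| Unknown start, ended 1 May 2018 | 20 Mar 2018 | concomitant, not prior |
| Start 2018, ongoing | 20 Mar 2018 | concomitant, not prior |
| Start Mar 2018, ongoing | 20 Mar 2018 | concomitant, not prior |
| Start 2015, ongoing | 1 Jan 2015 | prior and concomitant |
| Start Jan 2018, ongoing | 1 Mar 2018 (Screening) | prior and concomitant |
| Unknown start, ended 10 Mar 2018 | 1 Mar 2018 (Screening) | past |
| Start Mar 2018, ended 10 Mar 2018 | 1 Mar 2018 (Screening) | past |

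The first four rows are the problem cases. None of the rules asks whether the drug was already on record at Screening, so the result is the same for a drug taken for years and one begun on Day 1.

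**Which cases matter.** The wholly unknown start carries most of the point for long-standing therapy. The dosing-year case adds drugs begun earlier that year. The dosing-month case is the weakest, since a stable background drug will seldom have begun that month.

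**Weight of one record.** With 42 subjects randomized 1:1 there are about 42 / 2 = 21 per arm. Each subject whose drug is displaced lowers that drug's percentage in the arm's prior-and-concomitant table by 1/21 = 4.8 percentage points. This scales one record; it does not estimate how many there are.

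**Reach.** The primary mixed model (8.1.2) uses treatment, week, their interaction and Baseline score. The sensitivity analyses (8.1.3) and the Fisher tests on responders (8.3.6) do not use medication class either.

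**The case against.** The strongest defence is that the present rule errs towards showing possible on-study starts. A rescue or prohibited drug dated only to the dosing month appears as concomitant, and such drugs bear on the discontinuation criteria in protocol 6.4. A blanket rule calling every drug prior unless its partial date rules that out would hide some of them. This stands, and it limits the fix to drugs with documented predose use.

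Further points for the plan, all of which stand:

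- 4.2.7 says a same-day start is concomitant. It does not say concomitant only, a label 6.4.3 reserves for a start after the first administration. That the drug cannot be prior-and-concomitant follows from the definitions; the stronger label is an inference.
- 6.4.3 defines concomitant by use after dosing, and 6.4.4 assigns periods by use. Background therapy taken on study therefore still appears as concomitant. What is lost is its status as pre-existing.
- 6.2 identifies MG medication by indication and does not cite 4.2.7, so the Baseline summary may be unaffected.
- The rule is the same in both arms and reaches only descriptive output.

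The defence does not remove the core point. For a drug documented as in use before the first infusion, the plan's own definition of prior is met in fact and denied by the imputed date.

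**Conclusion.** The point holds in a narrow form. An ongoing medication with a wholly unknown start, or a start known only to the dosing year or, less often, the dosing month, is classed as concomitant and not prior-and-concomitant, even when predose use is on record. The prior-and-concomitant table by arm under-counts background MG therapy to that extent. Drugs dated to an earlier year or month, or stopped before dosing, are classified correctly. This is a minor correction to descriptive output and changes no efficacy result.

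Three stronger readings are tempting and are not supported:

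- A reader might infer that these records would count as protocol deviations for MG therapy started on study. SAP 3.4 and 5.2 identify important deviations by criteria in a separate document, through data cleaning and evaluation. Nothing derives them from imputed start dates.
- A reader might infer that the Baseline comparison in 6.2 is wrong. That follows only if 6.2 uses the imputed dates, which the SAP does not say.
- A reader might want a count of affected subjects. The documents give neither the number of background drugs per subject nor the rate of incomplete dates, so any count would rest wholly on assumed values.

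The conclusion assumes that 4.2.7 is programmed as written.

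**What to change.** Add a medication-specific rule to SAP 4.2.7: a medication with a missing or partial start date that was recorded as in use at Visit 1 or predose at Visit 2 is classed as prior, and also as concomitant if taken after the first administration of study drug. Keep the dosing-date imputation for adverse events and for medications first reported after dosing, so that possible on-study starts stay visible. In SAP 6.2, state that the Baseline MG-medication summary is based on documented predose use.

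The cost is a short paragraph in 4.2.7, a sentence in 6.2 and a small change to the derivation. The programmer must be able to tell from the data that a drug was recorded before dosing; the documents do not show the medication form, so this should be confirmed. There is essentially no statistical downside: a drug with documented predose use that continues on study remains in the concomitant data as well.

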AE=adverse event; BAFF=B-cell activating factor; BL=Baseline; BP=blood pressure; CSF=cerebrospinal fluid; CT=computed tomography; DNA=deoxyribonucleic acid; ECG=electrocardiogram; FV=Final Visit; GI=gastrointestinal; HIV=human immunodeficiency virus; IgA=immunoglobulin A; IgE=immunoglobulin E; IgG=immunoglobulin G; IGRA= interferon-gamma release assay; IgM=immunoglobulin M; IMP=investigational medicinal product; IRT=interactive response technology; LP=lumbar puncture; MG=myasthenia gravis; MGADL=myasthenia gravis-Activities of Daily Living; MGFA=Myasthenia Gravis Foundation of America; MRI=magnetic resonance imaging; PEOT=premature end of treatment; PK=pharmacokinetics; PR=pulse rate; RNA=ribonucleic acid; QMG=Quantitative Myasthenia Gravis; B; SFEMG=single fiber electromyogram; TB=tuberculosis; UV=Unscheduled Visit

^a Subjects will return to the clinic/hospital for Visits 15, 16, 18, and 20; for Visits 17 and 19 subjects will either return to the clinic/hospital, or, if possible and agreed by both the investigator and subject, have home visits conducted by certified healthcare professionals.

^b This visit is a telephone contact 24 hours post-IMP dose start.

^c Subjects who withdraw early will be encouraged to complete the PEOT Visit plus the FV (approximately 8 weeks after the final study drug administration).

^d A visit window of ± 2 days is allowed for the dosing visits. The visit window of ± 2 days is relative to the first dosing visit date. However, there should be a minimum interval of 5 days and maximum interval of 9 days as compared to the previous dose.

^e Includes consent for jitter (SFEMG) for the subjects consenting to this measurement at the participating sites. Additional informed consent is needed for participation in the exploratory genomic substudy.

^f Systolic and diastolic BP, pulse rate, temperature, and respiratory rate. On dosing days, vital signs will be measured prior to IMP administration, 15 minutes after the start of the infusion, at the end of the infusion, 2 hours after the end of infusion and 4 hours after the end of the infusion. At nondosing visits, vital signs need only be taken once during the visit.

Confidential

Page 29 of 193

- ^g Body weight at Screening and at Visit 9 will be used for calculation of dose; height will be assessed only at Screening.
- ^h In addition to Screening and the FV, a full neurological examination should be performed for any subject who experiences severe headache.

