2.3 Study design and conduct

This is a Phase 2a, multicenter, randomized, investigator- and subject-blind, placebo controlled, 2-arm, repeat dose, treatment sequence study evaluating the safety and efficacy of UCB7665 as a chronic-intermittent treatment for subjects with moderate to severe generalized MG.

Approximately 42 randomized subjects will be enrolled at approximately 30 sites from Europe, United States of America (USA), and Canada to achieve the targeted number of 40 evaluable subjects.

The maximum duration of the study per subject is approximately 18 weeks, consisting of a Screening Period (1 to 28 days), Treatment Period (6 weeks), and an Observation Period (8 Weeks).

Screening Period: The purpose of the Screening Period is to evaluate and confirm the subject's eligibility. The Screening Period should not exceed 28 days in total.

Treatment Period: The Treatment Period will consist of Dosing Period 1 followed by Dosing Period 2. Subjects will receive 3 doses of IMP at weekly intervals during each Dosing Period as follows.

- Dosing Period 1 will be 4 weeks, with 2 parallel Treatment Groups (UCB7665 7mg/kg or placebo).
- Dosing Period 2 will be 2 weeks, with 2 parallel Treatment Groups (UCB7665 7mg/kg or UCB7665 4mg/kg).

Prior to receiving an infusion with IMP, subjects will be assessed for efficacy measurements at each visit in the Treatment Period. All safety and efficacy measurements must follow the order specified in the Study Procedures Manual.

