Dosing Period 1: Dosing Period 1 will last for approximately 4 weeks (Day 1 to Day 28) and includes Visits 2, 3, 4, 5, 6, 7, and 8. Following completion of the Screening Period, eligible subjects will check-in at the clinic/hospital for the Randomization Visit (Visit 2). Subjects who continue to meet eligibility requirements will be randomized 1:1 to receive 7mg/kg of UCB7665 or placebo, administered by an approximately 30 minute sc infusion at weekly intervals for 3 weeks (Visits 2, 4, and 6) followed by an assessment visit at Week 4 (Visit 8). At Visits 2, 4, and 6 in Dosing Period 1, subjects will be required to remain in the clinic/hospital for at least 4 hours for safety monitoring after the infusion. Subjects may leave the clinic/hospital once the safety monitoring postdose period is over and the investigator or designee has no safety concerns. A follow-up telephone call will be conducted 24 hours postdose to assess the status of the subject (Visits 3, 5, and 7). Subjects will return to the clinic/hospital at Visit 8 for safety and efficacy assessments. The primary efficacy endpoint, change from Baseline in the QMG score, will be

[figure not shown]
assessed at the beginning of Dosing Period 2 at Visit 9 (Day 29) prior to rerandomization . The efficacy assessments that are performed at Visit 9 will therefore occur 2 weeks after the final dose of study drug in Dosing Period 1.

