3.2.2 Study periods

The maximum duration of the study per subject will be approximately 18 weeks, consisting of the following 3 periods:

- Screening Period: 1 to 28 days
- Treatment Period: 6 weeks
 - Dosing Period 1 of 4 weeks. This period will start at the first actual dosing of Period 1.
 - Dosing Period 2 of 2 weeks. This period will start at the first actual dosing of Period 2.
- Observation Period: 8 weeks

The end of the study is defined as the date of the final clinic/hospital visit of the final subject in the study.

In the case a subject does not receive dosing in Dosing Period 2, the rule for entering the Observation Period given in [Section 2.3](#) will be generalized such that the subject will enter the Observation Period the day after the last dosing of Dosing Period 1. All data up to the missed dose will be treated according to plan, including data planned on the dosing day prior to the actual dosing.

The following definitions for starting and entering the study periods will be applied:

- Started period 1 is defined as all subjects in the safety set. Completed period 1 includes those subjects who have completed assessments prior to the first study treatment of Period 2 (Day 29).
- Started period 2 is defined as having received treatment on Period 2 Day 29. Completed period 2 includes those subjects who have completed assessments on Observation Period Day 50.
- Started Observation Period is defined as having assessments on Observation Period Day 50. Completed observation period includes those subjects who have a completed status in the study termination case report form

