3.5.3 Safety Set

The Safety Set (SS) will consist of all subjects in the RS, who have received at least 1 dose of IMP.

Safety and immunological variables will be analyzed using the SS.

It is expected that subjects will receive treatment as randomized and hence safety analyses will be based on the randomized treatment group. However, if after unblinding it is determined that a subject has received the incorrect treatment based on the randomization schedule, then for safety analyses the subject will be allocated to the actual treatment they received in the respective Dosing Period.

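### AE duration with a missing start is counted from first UCB7665 rather than first IMP, so placebo-first subjects get negative, too-short or undefined values in the AE listing

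*SAP*

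**What the plan says.** SAP 4.2.7 contains two sets of rules for incomplete AE dates.

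- **Start-date imputation.** This is stated to serve two purposes: classifying AEs as treatment-emergent and classifying medications as prior or concomitant. Here, "If the start date is completely unknown, then use the date of first dosing". If that date falls after the known end date, the rule falls back to 1 January of the end year, or to the screening date if later.
- **Duration (Table 4-1).** In the row for a missing start day and time, duration runs from D0/T0 to the known end and is shown with a < sign. In the row with start and end both missing, it runs from D0 to the discharge day, with > for ongoing and < for resolved events. Both rows define the origin for Safety Set members identically: "D0 and T0 are the date and time of first administration of UCB7665". Only screen failures are treated differently, being counted from their screening visit. No other case is provided for.

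The Safety Set (SAP 3.5.3) is "all subjects in the RS, who have received at least 1 dose of" IMP, which includes placebo. In Dosing Period 1, subjects are "randomized 1:1 to receive 7mg/kg of UCB7665" or placebo (SAP 2.3). All subjects are rerandomized to one of two UCB7665 doses at Visit 9; per SAP 3.2.2, "Started period 2 is defined as having received treatment on Period 2 Day 29". SAP 3.1 also keeps a placebo group for subjects with no Period 2 dosing.

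**The concern.** Active-first subjects receive UCB7665 on Day 1, so first UCB7665 and first IMP coincide. In placebo-first subjects they are four weeks apart, and in placebo-only subjects the first of the two never happens. Applied as written, the duration rule can therefore return an impossible number, an upper bound below the true duration, or nothing, for subjects in the control group of a safety listing.

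The listing in SAP 11.2 prints duration together with days since first dose of IMP. Treatment-emergent status and period assignment also run from first IMP. The same event could thus be classified as though it began on Day 1 while its duration is counted from Day 29.

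**Working it through.** The plan gives no numerical example to reproduce, so the Table 4-1 formula is applied directly.

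**Inputs**
- Formula: duration = [(D2 - D0) × 24 + (T2 - T0)] / 24 days (SAP Table 4-1). With both dates missing: discharge day - D0.
- D0 for active-first subjects: Day 1.
- D0 for placebo-first subjects: Day 29 as planned. "A visit window of ± 2 days is allowed for the dosing visits" (Protocol Table 5.1, footnote d), so Day 27 to Day 31 is possible.
- Assumption for illustration: the AE ends at the same clock time as the infusion began (T2 = T0), so the formula reduces to D2 - D0.

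**Known end, missing start**

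| AE resolved on | D0 = Day 1 | Placebo-first, D0 = Day 29 | D0 = Day 27 | D0 = Day 31 |
|---|---|---|---|---|
| Day 20 | 20 - 1 = 19 | 20 - 29 = -9 | -7 | -11 |
| Day 40 | 40 - 1 = 39 | 40 - 29 = 11 | 13 | 9 |

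Each value is printed with a < sign. On the planned schedule the shift is always 29 - 1 = 28 days. Any event that ended before the first UCB7665 dose comes out negative.

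**Can the bound be false?** Yes. Take a placebo-first AE that truly ran from Day 10 to Day 35 but whose start was not recorded. It lasted 35 - 10 = 25 days. The rule prints 35 - 29 = <6 days. Anchored at first IMP it would print 35 - 1 = <34 days, which is true.

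**Both dates missing, discharge on Day 99.** Active-first: 99 - 1 = 98 days. Placebo-first: 99 - 29 = 70 days.

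**Placebo-only subject.** Assume the last dose was on Day 15 and the final visit 8 weeks later, on Day 71. There is no first UCB7665 administration, so D0 is undefined and neither row returns a value. Anchored at first IMP, the row with both dates missing returns 71 - 1 = 70 days.

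**AE that ended before any dosing.** AEs are collected from informed consent (SAP 11.2). If an AE with a missing start ended 3 days before the first infusion, an active-first subject gets -3 days and a placebo-first subject -3 - 28 = -31 days. Moving D0 to first IMP brings the second to -3 but leaves both negative. Table 4-1 has no equivalent of the fallback in the start-date rules.

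**The case against.** The best defence is that UCB7665 is loose wording for study drug. SAP 11.2 categorizes all AEs by relationship to UCB7665, which must cover events on placebo. SAP 7 refers to exposure to UCB7665 and points to section 11.1, which lists every administration in the Safety Set. Table 4-1 also assigns a D0 to every Safety Set subject and makes an exception only for screen failures, which makes sense only if first IMP was meant. This is plausible as to intent. It does not rescue the rule as written: the SAP's timing rules elsewhere refer to IMP or first dosing, its treatment groups keep placebo and UCB7665 apart, and a programmer following the table literally would produce the values above.

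Three stronger readings are tempting, and the documents do not support them.

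- *The SAP contradicts itself.* The first-dosing imputation is limited to classifying AEs and medications, and Table 4-1 is introduced separately for duration. Rules with different purposes need not share an origin. This is inconsistent anchoring, not a direct contradiction.
- *Only the placebo-first arm gets wrong values.* Events that ended before first dosing are negative in either arm.
- *Between-arm safety comparisons are distorted.* Protocol 14.4.1 says AE duration is listed only. None of the summaries in SAP 11.2 uses it, and no comparison of durations is planned.

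It is also fair to say that the trigger is narrow. AEs are asked about at each visit, with a telephone contact 24 hours after each dose, so missing start days may be few. A negative duration would also stand out beside the dates in the listing. A falsely short positive one would be harder to spot.

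**Conclusion.** The rule is wrong as written, and the consequence is minor. For placebo-first subjects it gives a negative duration when the event resolved before about Day 29, and a value 28 days too short (26 to 30 within the visit window) when it resolved later; with the < sign, that value can be a false upper bound. For placebo subjects never dosed in Period 2 it gives no value.

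The damage is confined to the AE listing and to events with a missing start day. Incidence, severity, seriousness, treatment-emergent status and period assignment are unaffected. The documents give no expected number of such events or of placebo-only subjects, so the number of affected listing lines cannot be estimated. The figures assume equal clock times for infusion start and AE end; other times move each value by less than a day.

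**What to change.** In both Table 4-1 rows, replace the reference to first administration of UCB7665 with first administration of IMP in Dosing Period 1. Every Safety Set subject then has a D0, and it is the same origin in both arms.

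Add one sentence for events whose end precedes D0, for example counting from the screening date, which the start-date rules in the same section already use as a fallback. Without it, pre-dose events keep negative durations in either arm.

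The cost is one phrase in two rows plus one sentence, and the matching line in the listing program. No data collection, analysis set or other output changes.
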